- Support and follow-up measures such as protocolized telephone follow-up and telemonitoring improve adherence. (Ruiz-López, 2009; Rotenberg, Murariu, Pang, 2016)
- The Adhesion Improvement Plan based on a cost-effectiveness balance achieves better adherence results. (Ibarra, Morillo, Rudi, Ventura, Navarro, 2013).

METHODOLOGICAL SECTION

1. Design. Experimental, prospective and controlled study. All participants will sign informed consent after knowing in depth the objectives, methods and risks of the study. The CONSORT Criteria for non-pharmacological trials will be followed (Boutron, Moher, Altman, Schulz & Ravaud, 2008).

2. Sample size: The sample size is defined by the research design, in which the subjects are randomly distributed to the two experimental conditions, that is, the Control Group and the PIMA Group. It is thus necessary to determine at the beginning the minimum size of the groups based on the following factors. Taking into account that the intervention process is based on the motivational interview, in the first place, we establish a type I error of 0.05, and a type II error of 0.20 (power = .8), as is usually assumed in research in the framework of the study of the therapeutic efficacy of motivational / psychological interventions (Hair, Anderson, Tathan & Black, 1999). On the other hand, reviews of previous research on the efficacy of motivational / psychological interventions on the outcome variables to be considered (behavioral change / adherence, quality of life), revealed that there are hardly any studies of this nature, without detail data on standardized effect size that serve as a starting point in defining, among other aspects, the ideal sample size for our research. Due to the characteristics of the existing studies (Edelman, Bell and Kidman, 1999; Edelman, Lemon, Bell and Kidman, 1999; Goodwin et al. 2001), we observed effect size values around 0.50. In addition, for a study such as the one proposed in this study, a sufficient number of subjects is required to allow observing and assuming the normality of the scores in the variables considered, as well as performing multivariate analyzes, with a sufficient number of observations to carry them out.

[figure not shown]

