finished. For all the above considerations, we conclude that around 33 subjects per group would be the size of the sample necessary to assess the therapeutic efficacy of the interventions developed. On the other hand, we take into account the type of patient we are dealing with, who may be abandoned, for which a number of 35 subjects per group is established (anticipating a certain experimental mortality). The design effect size as defined is $d = 0.60$, which is a moderate effect size.

3. Stages of the study:

3.1. Referral / recruitment phase and randomization. In patients diagnosed with OSA, 2 groups of at least 35 patients will be constituted. Following the CONSORT Criteria (Boutron, Moher, Altman, Schulz & Ravaud, 2008) for non-pharmacological trials, the randomization method has been selected through a simple method: each time the prescribers evaluate the sleep test, they include in one of the two groups according to the following randomization algorithm: each patient is assigned to a group alternatively, that is, one patient is assigned to the Control group and the next to the PIMA group; This sequence is followed in 6 pairs, being that the following 6 pairs were assigned starting with one patient to the PIMA group and another to the Control group later. This allocation mechanism is also the one used to compensate for experimental mortality in both groups. In this way 2 groups will be configured:

- 1) Control Group or PIMA 0, which will start treatment with regular CPAP WITHOUT stratification;
- 2) PIMA 1 Group, which will start treatment according to stratification; This will be the result of a comprehensive initial evaluation and the result of stratification.

3.2. **Stratification process:** To achieve stratification, two types of variables are taken into account that the bibliography indicates influence the treatment of CPAP: personal variables and modulating variables. Personal variables are those that refer to patient characteristics. These are grouped into 4 categories: protective factors, risk factors, clinical factors and motivation (in the case of OSA). The following figure shows the set of variables used for patient stratification, and their relationship with individualized protocols.

Regarding the modulating variables, these refer to the characteristics of both the patient's environment (distance between the patient's home and the hospital) or relative to options and

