The monitoring and visualization of the alerts will be carried out with a determined periodicity: Day 10, Day 20, Day 30 of the period after low adherence detection. The alerts (situations that imply poor evolution and need to notify the prescriber) are the following:

- - Hours <4
- AHI> X + Hours <4
- IAH> X + Hours> 4
- Leaks> Y

Prescribing physician information report: a report is extracted in PDF format that is reported to the prescribing physician.

3.1. Monitoring and control of adherence. All measurements will be performed in 4 times: Day 1 - Day 30 - Day 60 - Day 90 – Day 180. In the Control Group, the usual methodology of treatment with CPAP will be used. In PIMA 1 Group, the methodology will be used according to the Individualized Adherence Improvement Plan arising from stratification.

3.2. Analysis of results.

Descriptive variables (characterize the sample used and make the study replicable and transparent, thus contributing to generalization). Study of initial homogeneity: categorical variables (χ^2) + associated effect size. Quantitative variables: Student's t test for independent samples, correction (Levene's test).

- Hypothesis:
 - T-tests of means of related samples (to know if through the different interventions there are improvements in adherence and quality of life, they report the effects on the outcome variables)
 - Model of structural equations (to know the relationships between protection and risk factors and educational, training and technological actions)

- Independent samples t-test (know the significance associated with the differences between the two interventions)
- Analysis of variance (ANOVA) (differences were due to the type of intervention in combination with some other categorical variable)
- Linear correlations (know the interrelation between the so-called gains or aspects of change of the 2 interventions)
- Effect size:
 - or (Cohen's $d = t / rN$) (value exceeds 0.30, which is equivalent to a moderate-high effect size, greater in any case than 0.60)

3.1. Subjects of study.

Inclusion criteria: Being over 18 years of age, OSA diagnosis for whom CPAP treatment has been prescribed)

Exclusion criteria:

- Hypoventilation obesity
 - severe COPD
 - (FEV1 (%) = <50%)
 - mMRC > 2
 - Cognitive disorders
 - ICC (NYHA: Grade III and IV)
 - or reject

4. Variables

- **Sociodemographic variables:** age, gender, marital status, educational level, ...

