- **Clinical variables:** No. hours of CPAP use, IAH (TM), Leakage (TM), side effects.
- **Independent variables:** Stratification / Segmentation vs "SEPAR" Model.
- **Dependent variables:** adherence, quality of life.
- **Modulating variables:** PROFILE, protective factors, risk factors, motivation

ETHICAL ASPECTS AND MEASURES TO MAINTAIN THE CONFIDENTIALITY OF THE DATA

The prescribers and healthcare personnel participating in this Study undertake not to disclose in any way to third parties or to use Confidential Information of patients outside the study. Confidential Information shall be understood to be information that, regardless of its physical or digital medium or otherwise, is confidential (whether or not it is indicated therein or is derived from its nature) to the extent that:

1. is secret in the sense that it is not, as a body or in the precise configuration and assembly of its components, generally known or easily accessible to persons introduced into the circles in which the type of information in question is normally used;
2. has a commercial value because it is secret; and
3. has been subject to reasonable measures, under the circumstances, to keep it secret, taken by the person who legitimately controls it

The execution and development of the Study will give rise to access by healthcare personnel and prescribers to personal data of natural persons, especially patients, responsibility of the Hospital. That is why all of them expressly undertake to treat such data in compliance with the provisions of Organic Law 15/1999, of December 13, on Data Protection and other regulations that modify or develop this matter, and as of December 25 May 2018, in Regulation (EU) No. 2016/679, of April 27, 2016, guaranteeing the security, confidentiality and integrity of personal data that may be accessed or subjected to treatment within the framework of This studio.

The registration of the information will be carried out following the procedure of the Hospital Universitario de La Princesa, that is, all indications derived from internal regulations will be respected. The participants of this Study undertake to keep the strictest reserve and confidentiality regarding the Personal Data accessed during the execution of the Project work.

The main researchers undertake to implement the appropriate technical and organizational measures, in accordance with article 32 of the RGPD, to guarantee the security of Personal Data.

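### The planned correlation of gains does not say how the two arms are handled; if they are pooled and PIMA shifts both outcomes, the arm difference inflates the correlation

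*Combined protocol and SAP*

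**What the plan says.** In the combined protocol and SAP, the Analysis of results section (the second of two sections numbered 3.2) lists the methods as short bullets. One of them is "Linear correlations (know the interrelation between the so-called gains or aspects of change of the 2 interventions". It does not name the gains, the visits between which they are measured, the set of patients, or any adjustment for arm. The other bullets are a related-samples t-test for improvement in adherence and quality of life, a structural equation model, an independent-samples t-test between the interventions, and an ANOVA.

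The Variables section gives the dependent variables as "adherence, quality of life". The sample size section states "we observed effect size values around 0.50" for earlier studies and then "The design effect size as defined is $d = 0.60$, which is a moderate effect size". It sets 35 patients per group. Under the randomization section each patient belongs to one group only, Control or PIMA, in a 1:1 ratio.

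**The concern.** Gains under one intervention and gains under the other belong to different patients, so they cannot be paired and correlated with each other. The analyst has to choose a version that can be computed. One obvious choice is to correlate the gain in adherence with the gain in quality of life over all patients. That pooled coefficient mixes two things: how the gains go together among patients treated alike, and how far the arm means differ on both. If PIMA raises both means, the second part is positive whatever the first part is.

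At stake is interpretation. A significant pooled coefficient invites the conclusion that patients who gain more adherence gain more quality of life, when part of it may only restate that one arm did better on both. Because the choice between pooled and separate analysis is left open, it could also be made after the data are seen. At two-sided 0.05, significance needs |r| of about 0.235 with 70 patients pooled, but about 0.33 in one arm of 35.

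**Working it through.** **Inputs**
- 35 per group, 70 in all, 1:1 (sample size and randomization sections); 33 per group before the dropout allowance.
- Standardised effects of 0.50 and 0.60 (sample size section). The plan does not tie them to change scores or to quality of life. Applying them to both gains is an assumption made here.
- Type I error 0.05 (sample size section); sidedness is not stated, and two-sided is assumed.
- Within-arm correlation ρ is not given. Zero is used to isolate the artefact and 0.30 as an illustration.

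**The plan's own figures.** The documents give no figure for this correlation. The stated 33 per group is a separate matter: a two-sided independent-samples calculation at 80% power gives 44 (normal) or 45 (t) for d = 0.60. A one-sided test at 0.60 gives 35, and a paired two-sided t-test at 0.50 gives 34. Nothing below depends on which was meant.

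**Formula.** With 1:1 arms, unit within-arm standard deviations and effects d1 and d2 on the two gains, the arm difference adds d1·d2/4 to the covariance and d²/4 to each variance:

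r(pooled) = (ρ + d1·d2/4) / √[(1 + d1²/4)(1 + d2²/4)]

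**Size of the artefact, ρ = 0**
- d = 0.50 on both: 0.0625/1.0625 = 0.059.
- d = 0.60 on both: 0.09/1.09 = 0.083.
- d = 0.60 on one and 0 on the other: 0.

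**Rejection rates.** Simulation of bivariate normal gains, nominal two-sided 5%, ρ = 0, 35 per arm:

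| Effect on each gain | Pooled r | Pooled test rejects | Partial correlation given arm rejects |
|---|---|---|---|
| 0.50 and 0.50 | 0.059 | about 7.7% (7.5% to 7.7% between runs) | about 5% |
| 0.60 and 0.60 | 0.083 | about 10.5% | about 5% |
| 0.60 and 0 | 0 | 5.0% | about 5% |

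With 33 per arm and 0.60 on both gains, the pooled rate is 10.3%. A correlation within one arm alone also holds about 5% in every row.

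**Distortion when a real link exists**
- ρ = 0.30, d = 0.60 on both: (0.30 + 0.09)/1.09 = 0.358 instead of 0.30.
- ρ = 0.30, quality-of-life benefit entirely through adherence: d2 = 0.30 × 0.60 = 0.18. Then r = (0.30 + 0.027)/√(1.09 × 1.0081) = 0.327/1.048 = 0.31, close to 0.30.

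**Precision of the alternatives.** At ρ = 0.30 and 35 per arm, the partial correlation given arm has about 71% power. A correlation in a single arm has about 42%.

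**The case against.** The strongest reply is that the plan never says the arms are pooled. The bullet can equally mean a correlation within each intervention, and then the artefact cannot arise. The text is also a rough translation, which makes a close reading of one phrase fragile. This stands. A reader might infer that the plan defines an unadjusted pooled correlation, but the documents do not support that: they leave the point open.

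Three further objections hold in part.
- The two gains are inferred. The bullet names none, and no interval for a gain is given. Adherence and quality of life are nonetheless the only dependent variables listed, and the ones that the related-samples bullet tests for improvement.
- The null scenario is particular: PIMA must improve quality of life by a route that leaves it unrelated to adherence within arms. If the benefit runs through adherence, the distortion is negligible (0.31 against 0.30). It is also tempting to say that the false signal grows as PIMA becomes more effective. That is true only if both gains respond, whereas the Hypothesis and the main goal concern adherence.
- At the plan's effect sizes the bias in r is small beside the critical value of about 0.24. Much larger error rates need effects on both gains above anything that the documents propose.

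None of this supplies the missing specification. Nothing in the plan excludes the pooled version or removes arm from it.

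**Conclusion.** The point holds as under-specification of a supporting analysis, with a modest bias under one of its readings. If the arms are pooled and PIMA shifts both gains by 0.50 to 0.60, the pooled r is about 0.06 to 0.08 with no patient-level link, and the error rate is about 7.7% to 10.5% instead of 5%. This rests on four assumptions: pooling, the choice of adherence and quality of life as the gains, equal effects on both, and zero within-arm correlation. If the arms are analysed separately, or only one outcome responds, there is no inflation. The between-arm comparison of adherence has its own independent-samples t-test and is not touched. The point is minor, but the improvement is nearly free.

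**What to change.** In the Analysis of results section, name the two gains and the visits between which each is measured. Replace the simple linear correlation with the partial correlation of those gains given arm (70 − 3 = 67 degrees of freedom if all 70 patients contribute), and report the Control and PIMA correlations beside it.

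This removes the arm difference if pooling was intended, and is more precise than separate arm correlations if it was not. The cost is a line or two of text and one degree of freedom. No extra patients or data are needed.

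### The single formula labelled Cohen's d gives half of Cohen's d for the between-arm comparison, so the reported value is not on the scale of the design effect d = 0.60

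*Combined protocol and SAP*

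**What the plan says.** Under Analysis of results (numbered 3.2, in the Methodological section) the plan lists two kinds of t-test. One is within group: "T-tests of means of related samples". The other compares the arms: "Independent samples t-test (know the significance associated with the differences between the two interventions").

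A single effect-size entry closes the list. It names Cohen's d, prints the formula as t / rN, and adds the criterion "value exceeds 0.30, which is equivalent to a moderate-high effect size, greater in any case than 0.60". N is not defined, and the entry does not say which test it serves.

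The Sample size section (item 2) works on the between-group scale. It ends with "The design effect size as defined is $d = 0.60$, which is a moderate effect size", and for the arms it says that "a number of 35 subjects per group is established".

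**The concern.** Dividing t by the square root of the number of observations gives a standardised effect for a one-sample or paired test. It does not give Cohen's d for two independent groups. The main question of this trial is the difference between the Control and PIMA arms, and the trial's design effect is expressed as a between-group d. If the plan is followed as written, the report will carry a number called Cohen's d that cannot be set beside the design value of 0.60, or beside d from other trials, without a conversion that the label hides. With only one formula and one cut-off on the page, an analyst may also carry the 0.30 rule over to within-arm change, where it has a different meaning.

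**Working it through.** **Inputs.** Formula t / rN and the pair 0.30 / 0.60: Analysis of results. Design effect d = 0.60 and 35 per group: Sample size. Two assumptions are needed: rN is the square root of N, and the arms are equal in size (allocation is by alternation, so close to 1:1).

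**1. Which N reproduces the plan's own pair?** For an independent-samples test with n per arm, t = d × sqrt(n/2).
- With d = 0.60 and n = 35: t = 0.60 × sqrt(17.5) = 2.51.
- N as the total (70): 2.51 / sqrt(70) = 0.30. This matches the pair.
- N as the number per arm (35): 2.51 / sqrt(35) = 0.42. This does not match.
- With 33 per arm (total 66): t = 0.60 × sqrt(16.5) = 2.44, and 2.44 / sqrt(66) = 0.30, so the match does not depend on which of the plan's two group sizes is used.

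The total-N reading therefore fits the text.

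**2. Between arms.** Cohen's d = t × sqrt(1/n1 + 1/n2). With equal arms this is 2t / sqrt(N), so t / sqrt(N) = d/2.
- At 35 per arm and t = 2.51 (two-sided p = 0.014, 68 df): correct d = 2.51 × sqrt(2/35) = 0.60; the plan's formula gives 0.30.
- In 20,000 simulated trials with 35 per arm, the ratio of the plan's formula to d was 0.500.
- Modest imbalance hardly matters. In general the ratio is sqrt(n1 × n2) / N. For an illustrative 35 and 30 it is sqrt(1050) / 65 = 0.499.

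**3. Within one arm, if the line is applied there.** For n pairs, t / sqrt(n) = d_z, the mean change divided by the SD of the change. No factor of two arises.
- At n = 35, a value of 0.30 corresponds to t = 0.30 × sqrt(35) = 1.77 and d_z = 0.30 (two-sided p = 0.085, 34 df).
- In units of the raw SD, with equal SDs at the two times, d = d_z × sqrt(2(1 − rho)). The documents give no pre-post correlation rho. Over an assumed range of 0 to 0.9, 0.30 becomes 0.42 down to 0.13. It does not reach 0.60 anywhere in that range.

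**4. Precision.** For d = 0.60 with 35 per arm, SE = sqrt(2/35 + 0.60²/(2 × 70)) = 0.244, so the 95% CI is 0.60 ± 1.96 × 0.244, or 0.12 to 1.08.

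**The case against.** The strongest reply is that the plan itself states the conversion: it equates 0.30 on this index with more than 0.60, and 0.60 is the design value. This stands. A reader might infer that the between-arm threshold has been halved unnoticed, or that the trial will be judged against an effect half as large as planned. The documents do not support that. The fault is in the label and the reported number, not in where the between-arm threshold falls.

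The formula is also poorly legible and N is undefined. The 0.30 / 0.60 pair could have come from confusing a correlation with d: r = 0.30 converts to 2 × 0.30 / sqrt(1 − 0.09) = 0.63. This stands as a limit on certainty. The total-N reading is the likeliest one but is not proved. A mix-up of r and d would also leave the label wrong.

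The text never says that the formula or the cut-off covers the related-samples test. This stands too. It is inferred from the entry being the only one given. A reader might go on to infer that a non-significant within-arm change would be declared a success, but the plan does not make 0.30 a success rule, and size and significance are separate matters.

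Finally, a reader might see a contradiction between the moderate label in Sample size and the higher label in Analysis of results. The first describes d = 0.60 and the second describes values above it, so these are not two names for one value.

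None of these replies makes t / sqrt(N) a correct Cohen's d for two independent groups.

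**Conclusion.** The point holds as a wrong and ambiguous effect-size definition. Reading the formula as t / sqrt(N) with N the total and arms of equal size, the between-arm value reported as Cohen's d would be exactly half of Cohen's d: 0.30 where the true figure is 0.60. The within-arm part is conditional. If the same line is meant for the related-samples test, 0.30 there is d_z = 0.30 and the stated equivalence to 0.60 fails. If it is not meant for that test, the plan has no effect-size formula for within-arm change.

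The consequence is confined to reporting and interpretation. No test statistic, p-value or sample size changes, and a reader given t and the arm sizes could recover d. It should still be corrected, because the headline effect size would otherwise be misread against the design value.

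**What to change.** Replace the single entry with two definitions:

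- **Between arms:** d = t × sqrt(1/n1 + 1/n2), with t from the independent-samples test and n1, n2 the numbers analysed in each arm. Report it with its 95% CI, beside the difference in hours of CPAP use per night.
- **Within an arm:** t / sqrt(n), labelled as the paired effect size d_z, with n the number of pairs. Do not compare it with the between-arm d.

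Remove the shared 0.30 cut-off. Do not put the design value of 0.60 in its place as a pass mark: it is a planning assumption, and at 35 per arm an observed d of about 0.48 is already significant at the two-sided 5% level (critical t of 1.995 on 68 df × sqrt(2/35) = 0.48). Interpret the estimate through its interval and the difference in hours.

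The cost is a change of wording in the analysis section. It needs no new data and no change to conduct or sample size.
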